## 3. STATISTICS

For analysis of participants' anthropometric and metabolic characteristics, RT-PCR results and microbial richness and diversity measures, a Wilcoxon signed-rank test or paired samples *t*-test were used as appropriate with  $P < 0.05$  for significance and  $P < 0.1$  for reporting a trend (SPSS v.21). Statistical sequence analysis was based on differential abundance testing using the 'R' package DESeq 2 [16]. Differential abundance that occurred in test group subjects after dietary intervention but not in the control group was determined in a model with interaction (time, group and subject). Significance was reported for  $P < 0.05$  after multiple inference correction (Benjamini-Hochberg), and all OTUs with  $P < 0.05$  before correction were screened for trends. Initial microbial abundance differences between test group subjects who responded to dietary intervention with a 10 % plasma total cholesterol concentration drop and those without reduction were also tested with Deseq2 [16]. OTUs with  $P < 0.1$  after correction were considered significant. Alpha and beta diversity measures and PCoA of weighted UniFrac distances were calculated and plotted with Phyloseq [15].

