### 1.2. Hypothesis

1. 4- week consumption of beta-glucans alters the composition of intestinal microbiota and changes the ratio of different bacteria groups and consequently effects production of short chain fatty acids in a population with metabolic syndrome or with high risk for metabolic syndrome development.
2. 4- week consumption of beta-glucans has an influence on glucose metabolism and consequently improves insulin resistance within people with metabolic syndrome or with high risk for metabolic syndrome development.
3. 4 - week consumption of beta-glucans improves specific plasma lipid content in a population with metabolic syndrome or with high risk for metabolic syndrome development.

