## 2. STUDY METHODS

### 2.1. Trial design and participants enrolment

[figure not shown]
Study was performed as double blind, randomised, placebo controlled clinical trial and was performed regarding to CONSORT 2010 recommendations for randomised clinical trials [1]. The study was approved by the Republic of Slovenia National Medical Ethics Committee (112/08/13). Participant enrolment was performed within a national programme for metabolic disorder prevention in community health centres in Slovenia in association with family medicine doctors. Participants that met including criteria and had metabolic syndrome or high risk for metabolic development were suggested to participate in clinical trial.

Table 1: **INCLUSION CRITERIA**

Parameter	Inclusion criteria*
Age	30 – 70 years
Total cholesterol levels	$\geq 5.0 \text{ mmol/L}$
Waist circumference	Women $> 80 \text{ cm}$ Men $> 94 \text{ cm}$
And presence of at least one of the remaining determinants for MS	
HDL-cholesterol	Women $< 1.29 \text{ mmol/L}$ Men $< 1.03 \text{ mmol/L}$
Raised blood pressure	Systolic blood pressure $\geq 130 \text{ mm Hg}$ Diastolic blood pressure $\geq 85 \text{ mm Hg}$
Raised fasting plasma glucose	$\geq 5.6 \text{ mmol/L}$

\*Participants diagnosed with metabolic syndrome and meeting the age criteria were directly included in the study. Exclusion criteria were diabetes type II, thyroid disorders, kidney disorders and antibiotic treatment.

Participants who met the inclusion criteria started the intervention after agreement with study conditions and procedures. Participants that agreed to participate were randomised and enrolled in trial as the control or test group (Figure 1).

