**Figure 1: Participants flow diagram.**

## 2.2. Dietary intervention

Participants consumed bread with beta-glucans content of approximately 3,4 g beta-glucans per 100 g of bread in 4-week long intervention. Before study participants had two-week washout period without consuming any pre- and pro-biotics. Participants retained their usual eating habits during the

intervention. A 72-hour dietary recall was performed in order to control participants' diet and eating habits. Participants were told to consume 200 g of bread daily, not knowing whether the bread was experimental or control. Participants included in the test group consumed 200 g of BGB, containing more than 6 g of barley beta glucans, daily. Participants in the control group consumed 200 g of CWB without added beta glucans. 72-hour dietary recall was performed before intervention and at the end of the trial to evaluate daily nutrient and energetic input of each participant.

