#### 2.3.2. Oral glucose tolerance test (OGTT)

OGTT was performed one day before and one day after the four-week intervention [7]. Participants fasted overnight (for at least 10 hrs). Fasting blood samples were obtained for analysis of baseline glucose and insulin levels. After the consumption of glucose solution (75 g of glucose dissolved in 250 ml of water) in five minutes time, blood samples were taken, at 30, 60 and 120 minutes. Concentrations of blood glucose were determined with a standardised spectrophotometric methodology (Roche Hitachi Cobas c system (GLUC3)). The procedure is based on hexokinase and glucose-6-phosphate dehydrogenase reaction [8]. Blood insulin was determined by immunoradiometric assay (Biosource Europe S.A., Nivelles).

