#### 2.3.4. Microbial community analysis

**DGGE:** PCR-DGGE fingerprinting was performed to check the quality of isolated DNA between parallel samples and to compare the individual profiles. PCR-DGGE analysis was performed as described by Matijašić et al. (2014) [10].

**Real-time PCR analysis** was performed by an established procedure for quantification of bacteria in faecal samples [10] with slight modifications using a ViiA™ 7 Real Time PCR System (Applied Biosystems, USA). Data were analysed with ViiA™ 7 Software 1.2.2 (Applied Biosystems, USA).

**Next generation pair end sequencing:** For 16S rRNA sequencing, 23 participants were chosen randomly among those with both samples qualified for sequencing after DGGE examination. In total, 46 samples from 14 persons in the test group and nine persons in the control group were examined.

The Illumina Miseq platform with v.3 2x300 pair end technology was used for sequencing V3 and V4 16S rRNA regions (Microsynth). After demultiplexing, raw reads were processed following the UPARSE pipeline (Usearch v.8, June 2015) [11]. Stringent quality filtering based on a low expected number of errors was used for OTU formation with algorithm parameters optimized after mock sample analysis (34 strains). With relaxed quality filtered sequences, more than 91 % of raw reads could be placed into an OTU with a 0.03 distance criterion. Presumptive OTU identity was determined with the 'usearch\_global' function searched against Silva NR SSU v.119 and LTP SSU type strains v.121 database. Taxonomy was assigned to OTUs with Wang et al.'s (2007) [12] method implemented in Mothur v.1.35 and the RDP training set 14 [13]. FastTree2 was used for the generation of an approximately maximum-likelihood phylogenetic tree [14]. Taxonomy, the OTU table and the phylogenetic tree were handled with the 'R' package Phyloseq for statistical analysis and graphics [15].

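### Metabolic, anthropometric, RT-PCR and diversity outcomes get only paired before/after tests, so most of the hypotheses are never tested against the control bread

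*SAP*

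**What the plan says.** SAP section 2.1 describes the design: "Study was performed as double blind, randomised, placebo controlled clinical trial". Participants were allocated to test or control bread, and no matching is described.

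The hypotheses in section 1.2 attribute effects to beta-glucans. Hypothesis 2 is that their consumption "has an influence on glucose metabolism and consequently improves insulin resistance", and hypothesis 3 that it "improves specific plasma lipid content in a population with metabolic syndrome". Hypothesis 1 concerns microbiota composition and short-chain fatty acids.

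For anthropometric and metabolic characteristics, section 3 continues: "RT-PCR results and microbial richness and diversity measures, a Wilcoxon signed-rank test or paired samples" t-test, with P<0.05 as significant and P<0.1 as a trend. It names no two-sample test, ANCOVA, mixed model or group-by-time term for these outcomes.

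The control group enters the inference in one place only, the DESeq2 analysis, where differential abundance "was determined in a model with interaction (time, group and subject"). The cholesterol-responder analysis stays inside the test group. Beta diversity and PCoA are calculated and plotted, with no group test named. The protocol has before/after recording tables but no statistics section.

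**The concern.** The reason to randomise to a control bread is to separate the effect of beta-glucans from everything else that happens over four weeks. A before/after test does not make that separation. Any change common to both arms counts as a finding in the test arm.

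The plan itself suggests possible sources of a common change. Section 2.2 applies the same instruction to both arms: "Participants were told to consume 200 g of bread daily". Table 1 in section 2.1 admits some participants on thresholds, for example total cholesterol of at least 5.0 mmol/L, so regression to the mean is possible where a qualifying value also serves as baseline. Neither source is shown to have operated, but a paired test could not tell either from a beta-glucan effect.

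There is also no rule for turning paired P values into a conclusion. If the tests were run by arm, a significant result in one arm and a non-significant one in the other is not a test of the difference. The error can also go the other way: a real difference between breads could be overlooked because both arms changed significantly.

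At stake are all of hypotheses 2 and 3 and part of hypothesis 1, for which the plan yields no estimate, confidence interval or P value for one bread against the other.

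**Working it through.** **No planned figure to reproduce.** The readable text gives no sample-size calculation, effect size or SD. The core point rests on the text; the arithmetic only shows what can follow from it.

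**Inputs**
- Arm sizes: section 2.3.4 states that "46 samples from 14 persons in the test group and nine persons in the control group were examined". This is the sequenced subset. Full-trial arm sizes are not in the readable text (the flow diagram is not shown), so 20/20 and 30/15 are added as assumptions.
- Levels: 0.05 and 0.1 (section 3). Sidedness is not stated; two-sided is assumed.
- Shared shift d, in SDs of the change: 0.1, 0.25 and 0.5, all assumed. The true difference between breads is set to zero.

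**Step 1: paired t-test in one arm.** The test statistic is noncentral t with n − 1 degrees of freedom and noncentrality d√n. The rejection probability is P(|T| > critical value). For n = 14 and d = 0.5, the noncentrality is 0.5 × √14 = 1.87, which gives 0.410. For n = 9, it is 0.5 × 3 = 1.5, which gives 0.263.

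**Step 2: significant in one arm only.** The arms are independent, so test-only = p14 × (1 − p9) and control-only = p9 × (1 − p14). At d = 0.5 these are 0.410 × 0.737 = 0.302 and 0.263 × 0.590 = 0.155.

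| Shared shift (SD) | Test arm P<0.05 | Test arm P<0.1 | Control arm P<0.05 | Test only | Control only |
|---|---|---|---|---|---|
| 0.1 | 0.064 | 0.121 | 0.058 | 0.060 | 0.054 |
| 0.25 | 0.140 | 0.230 | 0.102 | 0.125 | 0.088 |
| 0.5 | 0.410 | 0.551 | 0.263 | 0.302 | 0.155 |

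With no shift at all, test-only occurs with probability 0.05 × 0.95 = 0.0475.

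**Step 3: other arm sizes** (100,000 simulated trials per setting, no beta-glucan effect)

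| Test/control | Shift (SD) | Test arm P<0.05 | Test only | Two-sample t on change |
|---|---|---|---|---|
| 20/20 | 0.25 | 0.186 | 0.151 | 0.050 |
| 20/20 | 0.5 | 0.566 | 0.249 | 0.050 |
| 30/15 | 0.25 | 0.263 | 0.223 | 0.050 |
| 30/15 | 0.5 | 0.754 | 0.426 | 0.050 |

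The problem does not depend on unequal arms.

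**Step 4: between-arm test at 14/9.** In 40,000 simulated trials with a pre/post correlation of 0.7 and shifts of 0.1, 0.25 and 0.5 SD, ANCOVA rejects in 0.050, 0.051 and 0.049. The change-score t-test rejects in 0.051, 0.052 and 0.051.

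**Step 5: what the between-arm test can detect at 14/9.** The standard error, in SDs of change, is √(1/14 + 1/9) = 0.427. The 95% CI half-width is 2.080 × 0.427 = 0.889 SD. Power for a 0.5 SD difference in change is 0.201 (change score), or by simulation 0.244 to 0.206 with ANCOVA at correlations of 0.5 to 0.8. The change-score test reaches 80% power at 1.255 SD.

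**The case against.** Nobody can point to a between-arm test for these outcomes, so the case on the other side is about overstatement.

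- *Section 3 does not say the paired tests were run by arm.* True; that is an inference. It does not rescue the plan, because a pooled before/after test would not compare the breads either. Only the point about combining two P values depends on it.
- *The 14/9 split belongs to the sequenced subset.* This stands. Among the affected outcomes, only sequence-based richness and diversity plausibly have those sizes. For lipids and glucose, the 14/9 power and precision figures establish nothing, which is why other sizes are shown.
- *The shared shift is assumed.* This stands too. At 0.1 SD the test-only rate is 6.0% against 4.75% with no shift, which is negligible. Section 2.2 also says that usual eating habits were kept, so a bread-related shift is conjecture. But the error rate should not hang on an unknown shift when the control arm was included to remove it.
- *ANCOVA is a preference.* Fair: a change-score comparison holds 5% as well, and ANCOVA gains only a few points of power in these settings.
- *Short-chain fatty acids and insulin resistance need attention as well.* Agreed. Section 3 names no test for short-chain fatty acids unless they count as metabolic characteristics, and glucose and insulin curves alone do not give a measure of insulin resistance.

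**Conclusion.** The concern holds and must be fixed before any efficacy conclusion is drawn from these outcomes. As written, hypotheses 2 and 3 and the RT-PCR and diversity part of hypothesis 1 are not tested against control bread. That follows from the wording of section 3 and needs no assumption. The sequence-abundance part of hypothesis 1 is not affected.

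The size of the harm is conditional. With normally distributed changes, shared shifts of 0.25 to 0.5 SD and no true effect, the test-arm paired test is significant in 14% to 41% of trials at 14 participants, and in 26% to 75% at an assumed 30. A between-arm test holds about 5% per outcome throughout.

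**What to change.** Section 1 of the SAP says that it was prepared after the trial had finished, so the paired tests cannot be replaced prospectively. Add a paragraph to section 3, labelled as a post hoc between-arm analysis:

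- For each lipid, glucose, insulin, anthropometric, RT-PCR and richness/diversity outcome, and for short-chain fatty acids, fit ANCOVA of the four-week value on randomised group with the baseline value as covariate. Use a log transformation or a rank-based version if skewed. A comparison of change scores is an acceptable alternative.
- Include all randomised participants with both values, analysed as randomised. Report n per arm and the between-arm difference with 95% CI and P value.
- In the OGTT, after the fasting sample, "blood samples were taken, at 30, 60 and 120 minutes". Name one summary for glucose and one for insulin, for example the 0–120 minute area under the curve, so that four time points do not become eight tests. Also name the insulin-resistance measure that hypothesis 2 refers to.
- Keep the paired tests as a record of what was done, mark them descriptive, and state that no efficacy conclusion rests on them.

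The cost is one paragraph and a re-analysis of data already collected. Some paired results now called significant may not survive. The added analysis remains post hoc, and its 5% applies per test, not across outcomes. In the sequenced subset, power for a 0.5 SD difference is about 20%, so a null result there would be inconclusive and should not be reported as absence of effect.

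### Scalar outcomes are tested at an uncorrected P<0.05 with a P<0.1 trend tier and no deciding outcome, while Benjamini-Hochberg is stated only for the OTU tests

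*SAP*

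**What the plan says.** SAP section 3 treats "anthropometric and metabolic characteristics, RT-PCR results and microbial richness and diversity measures" as one group. They are analysed by paired t-test or Wilcoxon signed-rank test, with P<0.05 as significance and P<0.1 "for reporting a trend (SPSS v.21"). No correction is stated for this group.

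The same paragraph handles the sequence data differently. Differential abundance "was determined in a model with interaction (time, group and subject"), and significance there is P<0.05 "after multiple inference correction (Benjamini-Hochberg"). Two looser OTU rules follow. OTUs with P<0.05 "before correction were screened for trends". In the comparison of cholesterol responders with non-responders, OTUs with P<0.1 "after correction were considered significant".

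No ranking of outcomes makes up for the missing correction. SAP section 2.3 puts the four lipids, insulin resistance and the microbiota work under one primary heading. Section 2.4 defines the secondary outcomes as the same measurements repeated after 4 weeks, so the two labels mark time points and not priority. Section 1.2 lists three hypotheses. On lipids, it says that the product "improves specific plasma lipid content in a population with metabolic syndrome" (or at high risk of it), without naming a lipid. On glucose, it says that the product "has an influence on glucose metabolism and consequently improves insulin resistance", without naming an OGTT measure or an index.

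**The concern.** Each valid single test keeps its own 5% error rate. The difficulty is at the level of the hypothesis: any of several outcomes could be taken as support, so the chance that at least one is positive by luck exceeds 5%, and counting P<0.1 as a trend raises it further. The number of scalar tests is not stated, so a reader of the results cannot tell how many tests lie behind a reported effect. The plan corrects for multiple testing among OTUs, so the problem was recognised, but the correction was not carried over to the lipid and glucose outcomes that two of the three hypotheses concern.

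**Working it through.** The documents give no overall error rate to reproduce. The only stated quantities are the thresholds 0.05 and 0.1. What follows sizes the consequence under assumptions.

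**Counts.**
- Four lipids (SAP section 2.3).
- Weight and waist (protocol part B, table 1). Blood pressure is left out because its after-intervention cell holds a slash.
- Glucose and insulin at 0, 30, 60 and 120 minutes, 2 x 4 = 8 values (protocol OGTT table).
- Hence 4 lipids alone; 4 + 2 + 2 = 8 if each OGTT curve is reduced to one summary; 4 + 2 + 8 = 14 if each time point is tested.

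None of these is an upper bound. RT-PCR targets, diversity indices, an insulin-resistance index or the three short-chain fatty acids would add tests. The fatty acids are in the protocol and in hypothesis 1, but SAP section 3 does not name them.

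**Uncorrected tests.** Assume two-sided tests (the SAP does not state sidedness), one per outcome, and no true change in the tested contrast. For m independent tests the chance of at least one positive is 1 - (1 - alpha)^m. For example, 1 - 0.95^4 = 0.185 and 1 - 0.95^14 = 0.512. For correlated tests I used normal statistics with a common pairwise correlation rho.

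| Tests | P<0.05, rho 0 / 0.3 / 0.5 / 0.7 | P<0.1, rho 0 / 0.3 / 0.5 / 0.7 |
|---|---|---|
| 4 | 0.185 / 0.174 / 0.156 / 0.130 | 0.344 / 0.322 / 0.288 / 0.241 |
| 8 | 0.337 / 0.300 / 0.250 / 0.191 | 0.570 / 0.514 / 0.435 / 0.337 |
| 14 | 0.512 / 0.438 / 0.348 / 0.249 | 0.771 / 0.690 / 0.573 / 0.423 |

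For the four lipids in the favourable direction only, the chance is 6.5-9.6% at P<0.05, against 2.5% for one two-sided test in that direction. If paired tests are run in each arm, 14 outcomes give 28 tests and 44-76% (1 - 0.95^28 = 0.762 at rho 0).

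**Benjamini-Hochberg at 5%, nothing truly different.** The chance of any rejection is 4.1-5.0% for 4 tests, 3.7-5.0% for 8 and 3.3-5.0% for 14.

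**Benjamini-Hochberg at 5%, some effects real.** Suppose that all four lipids truly shift and the rest of the family does not. The chance of at least one false rejection among the nulls (simulation, rho 0.7 to 0) is:

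| Family | Shift 2.8 SE | Shift 4 SE |
|---|---|---|
| 9 tests, 5 null | about 6-10% | about 8-13% |
| 14 tests, 10 null | about 6-12% | about 8-16% |

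Real lipid effects raise the threshold that the remaining outcomes have to meet.

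**Families by hypothesis.** With assumed scalar families of 4 lipids, 2 OGTT summaries and 3 short-chain fatty acids, each at 5%, the chance of any positive over the three is 9-14% under no effect (1 - 0.95^3 = 0.143 at rho 0). This leaves out the OTU interaction analysis, which already serves hypothesis 1 at 5%. Adding a scalar family brings hypothesis 1 to as much as 1 - 0.95^2 = 9.8% if the two are independent. All four families together give 1 - 0.95^4 = 18.5% if independent.

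**Power.** If one outcome truly differs and has 80% power uncorrected (a 2.80-SE shift), its power becomes about 62% in a family of four and 53% in a family of eight. The smallest thresholds are 0.05/4 = 0.0125, 0.05/8 = 0.0063 and 0.05/14 = 0.0036.

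**The case against.** The plan keeps significance and trend apart, and uncorrected OTUs are only screened, so neither loose tier is called significant. That stands; only the responder rule applies the word significant at 0.1. The SAP was also written after completion (section 1), so no error control can now be prospective. That stands too, and it argues for disclosure. An openly exploratory study may reasonably leave P values unadjusted, but section 1.2 states directional hypotheses and section 3 declares significance, so this plan does not present itself as exploratory.

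A second objection is that the percentages do not model the planned tests. They assume one test per outcome and no change in the tested contrast, whereas paired before-after tests may be run in each arm and may show change without any product effect. That is fair, so the figures are illustrations. A reader might take 25-51% as this trial's actual error rate, or infer that its positive findings are false. The documents support neither, since they give no test count, no correlations and no results in the text reviewed.

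A third objection is that comparing arms is a separate issue from multiplicity. It is, but the two meet in the remedy: adjusting before-after P values would not help if both arms change over time or regress to the mean, which is possible because Table 1 enrols on total cholesterol of at least 5.0 mmol/L.

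Finally, it is tempting to promise that Benjamini-Hochberg would hold the chance of any false positive at about 5% overall, or at 5% per hypothesis. The first is true only if nothing in the family differs, and the protocol introduction itself says that beta-glucans improve lipid and glucose metabolism. The second overlooks the OTU family already attached to hypothesis 1.

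**Conclusion.** The concern holds as a gap in what can be claimed, and it is cheap to repair. The absence of correction is read from the SAP's silence on the scalar tests, beside an explicit correction for OTUs in the same paragraph. The chance of at least one chance finding clearly exceeds 5% under every count and correlation tried, but its exact size rests on those assumptions. False discovery rate control is a proportionate remedy that must not be described as a 5% family-wise guarantee: with four real lipid effects in an assumed family of 9 or 14, the range is about 6-16%. Single tests are not invalidated. It is an improvement that should be made, held with medium confidence.

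**What to change.** 1. Base the scalar conclusions on test-versus-control contrasts of change, in line with the interaction model already used for OTUs. Report every test, the number of tests, a 95% CI and a Benjamini-Hochberg adjusted P value within a stated family. Call this false discovery rate control at 5% and state the limit described above. If the families follow the section 1.2 hypotheses, say that hypothesis 1 also carries the OTU family, and that the 9-14% over three scalar families does not include the OTU tests. Weight and waist belong to none of the three hypotheses, so place them in an all-outcome family or report them as supportive.
2. Label the P<0.1 tier, the uncorrected OTU screen and the 0.1-level responder analysis as hypothesis-generating.
3. Disclose the chosen families and any OGTT summary as post hoc.

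The work is re-analysis of existing data and report wording. The price is stricter thresholds with the power loss shown above, and trend results can no longer be offered as evidence. Families by hypothesis cost less power than one pooled family but leave a higher overall error rate. Prespecification cannot be restored.

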## 2.5. Missing data

Due to complex presentation of data for changes in gut microbiota composition, we can't provide results for primary and secondary outcome measure of microbiota composition.

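### The OTU interaction test shows that the two breads' before-after changes differ; it cannot show that an OTU changed in the test group and stayed unchanged in controls

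*SAP*

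**What the plan says.** SAP section 3 (Statistics) analyses the sequencing data with DESeq2 and states what the model is meant to deliver: "Differential abundance that occurred in test group subjects after dietary intervention but not in the control group was determined in a model with interaction". The model is described only as "in a model with interaction (time, group and subject". No design formula, tested coefficient or within-arm follow-up is given. Significance is declared at P < 0.05 after Benjamini-Hochberg (BH) correction. A looser tier is added: "all OTUs with $P < 0.05$ before correction were screened for trends".

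Section 2.3.4 gives the numbers: "46 samples from 14 persons in the test group and nine persons in the control group were examined". Section 2.2 describes the comparator: "Participants in the control group consumed 200 g of CWB without added beta glucans". The test group also ate 200 g of bread daily. Section 2.5 says of the findings that "we can't provide results for primary and secondary outcome measure of microbiota composition". The protocol lists the microbiota methods but contains no analysis plan.

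**The concern.** The conclusion in section 3 has two parts: the OTU changed under beta-glucan bread, and it did not change under control bread. The interaction establishes neither part alone. It is sensitive only to the gap between the two arms' changes, and that gap can arise while the test arm stays flat.

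This matters because the interaction is the only between-arm microbiota test that the SAP names. The other microbiota measures in section 3 get paired tests, and the cholesterol-responder comparison is made within the test group. The interaction therefore carries the randomised evidence for Hypothesis 1 in section 1.2. Applied as worded, the rule could list a control-driven OTU as a change in the test group. It could also describe an OTU that moved in both arms, but further in one, as unchanged in controls.

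**Working it through.** **Inputs.** From SAP 2.3.4: 14 test and 9 control participants, two samples each, 2 × (14 + 9) = 46, which agrees with the stated total. From SAP 3: alpha 0.05. The documents give no sidedness, effect size, SD of change or power, so there is no design figure to reproduce. Assumed: two-sided tests, Gaussian log-abundance changes, and SD of within-person change 1 in both arms. A two-sample t-test on changes stands in for the DESeq2 interaction; it is not a negative binomial fit.

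**Step 1: the two hypotheses.** Let μT and μC be the mean before-after log changes in the test and control arms.

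- Null of the interaction: μT − μC = 0.
- Conclusion in the SAP: μT ≠ 0 and μC = 0.

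Rejecting the first does not give the second. Only the difference enters the test, so any pair (μT, μC) with the same absolute difference is flagged equally often. This holds whatever the SD.

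**Step 2: normal approximation.** SE = √(1/14 + 1/9) = √0.1825 = 0.427. For a difference of 1 SD, 1/0.427 = 2.34, and the rejection probability is Φ(2.34 − 1.96) ≈ 65%. For 0.5 and 1.5 SD it is about 22% and 94%.

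**Step 3: simulation with t-tests** (50,000 or 100,000 trials per row, unadjusted 0.05).

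| True change, test / control (SD) | Interaction flagged |
|---|---|
| 0 / 0 | 4.9% |
| 0 / 0.5 | 20.1% |
| 0 / 1.0 | 60.9% |
| 0 / 1.5 | 91.6% |
| 1.0 / 0 | 61.0% |
| 1.5 / 0 | 91.8% |
| 0.5 / −0.5 | 60.6% |
| 1.5 / 0.5 | 60.6% |

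Every row with a difference of 1 SD gives about 61%, whichever arm moved. Among flagged OTUs in the three control-only rows (0.5, 1.0, 1.5 SD), 89.8%, 95.4% and 95.7% show no significant within-test change.

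**Step 4: could non-significance in controls supply the second part?** A paired t-test in nine people has power 26.3% for a 0.5 SD change and 74.8% for 1 SD. It would miss them 73.7% and 25.2% of the time. Equivalently, the 95% CI half-width at SD 1 is 2.306 × 1/√9 = 0.77 SD, so even an observed change of zero is compatible with a sizeable shift.

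**Step 5: after BH at 0.05.** Assume 300 OTUs, of which 30 move 1.5 SD in the test arm only, and vary the number that move 1.5 SD in the control arm only.

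| Control-only OTUs | Share of significant OTUs with no test-arm change |
|---|---|
| 0 | about 5% |
| 5 | about 18% |
| 10 | about 28% |
| 30 | about 52% (22.9 of 43.9 on average) |

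BH does not remove the control-driven hits, because for the interaction null they are true rejections.

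**The case against.** The strongest reply is that the test is right and only a sentence is loose. Under randomisation, a true interaction is an effect of beta-glucan bread relative to control bread, even if the test arm stayed flat. It therefore bears on Hypothesis 1 whichever arm moved, and its sign is correct as a relative difference. That stands, and it is why the test should not be replaced.

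A second reply is that control-only movement may be uncommon. Both arms ate 200 g of bread daily, so a shift due simply to eating bread is shared and cancels in the interaction. A control-only shift would need beta-glucans to offset a change seen in controls, or some other difference between the breads that the documents do not describe. That also stands. It limits how often the problem would arise, but it does not make the inference valid.

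Third, section 3 does not name the contrast, and a model with these terms can also yield arm-specific time effects. An unreported within-arm check cannot be excluded. Equally, none is described.

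A reader might go further and infer that OTUs moved only by the control bread have been reported as beta-glucan changes. The documents do not support that: section 2.5 withholds the microbiota composition results, so no OTU, direction or attribution can be examined. Nor do the rejection rates in the working show an inflated type I error. They are power against a real difference between arms; with no change in either arm the rate is 4.9%.

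**Conclusion.** The point holds as a fault of inference, not of test choice. Section 3 attaches an arm-specific conclusion to a test of the difference in change, and no other section adds a step that would justify it.

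The equal sensitivity to test-only and control-only shifts is algebraic. Its size is illustrative: about 20%, 61% and 92% of control-only shifts of 0.5, 1.0 and 1.5 SD would be flagged, on assumed Gaussian changes with SD 1 at unadjusted 0.05. After BH, the share of hits with no test-arm change runs from about 5% to 52% as the assumed number of control-only OTUs goes from 0 to 30. That range depends almost wholly on a mix the documents do not reveal, so no single figure from it should be quoted. What can be said is that misattribution could occur under the rule as written, not that it did.

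**What to change.** Keep the interaction model and the BH-adjusted P < 0.05. In section 3:

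- State the DESeq2 design formula and the exact contrast tested.
- Describe significant results as OTUs whose before-after change differed between test and control bread.
- For each, report the interaction log2 fold change and both arm-specific before-after log2 fold changes, all with 95% CIs from the same fitted model.
- Say which arm moved by reference to those estimates, and treat that statement as descriptive because the OTUs were selected on the interaction.
- Drop the claim of no change in controls as a conclusion.

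Do not add a second BH step on the test-arm contrast within the interaction-positive set. Selection and the follow-up test share the test-arm data: their correlation is √[(1/14)/(1/14 + 1/9)] = 0.63. Among OTUs null in both arms but selected at unadjusted 0.05, about 28% would then pass a same-direction test-arm test at 0.05, so the nominal error rate would not hold.

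The cost is a few lines of SAP text and two further contrasts per OTU from a model already fitted, with no new data. The downside is that fewer OTUs can be described as changed by beta-glucans in the test group.
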